5.0 CTN-0051 OBJECTIVES

5.1 Primary Objective

The primary goal of the study is to estimate the difference, if one exists, between XR-NTX and BUP-NX in the distribution of the time to relapse (i.e., loss of persistent abstinence) during the 6-month trial.

The primary outcome measure is the time to the event, with the event called relapse. By definition individuals are abstinent at the time of randomization. Relapse occurs if the participant is using any non-protocol prescribed opioids regularly starting at day 21 post-randomization or thereafter. Operationally, relapse is defined as either: (a) four consecutive opioid use weeks, or (b) seven consecutive days of use by self-report. A use week is defined as any week during which a participant self-reports at least one day of use during that week, provides a urine sample positive for non-protocol opioids, or fails to provide a urine sample. Self-report of opioid (heroin or prescription opioids) and other substance use is ascertained at each weekly study visit using the Timeline Follow-Back for each day leading back to the previous visit. Urine is collected at each study visit and tested for opioids. In the event that a participant reports no use, but their urine test indicates use, the week is considered a use week. Missing urine samples are classified as positive. The time of the event occurs at the start of the qualifying clinical event period (e.g., first of the 7 consecutive use days or start of the 4 consecutive weeks of use).

5.2 Secondary Objectives

Secondary objectives are to:

1. Compare outcome on XR-NTX versus BUP-NX for the following domains:
 - a. Proportion successfully inducted onto assigned medication.
 - b. Safety, as measured by adverse events and serious adverse events, including opioid overdose episodes, both during the 6-month trial and during the 3-month follow-up period.
 - c. Opioid abstinence, as measured by the Timeline Follow-Back (TLFB) (self-report days using opioids), proportion of opioid-positive urine tests.
 - d. Misuse of alcohol and other drugs of abuse (e.g., cocaine, other stimulants, cannabis, benzodiazepines), by self-report and urine drug screens.
 - e. Tobacco use, as measured by the Fagerström Test for Nicotine Dependence (FTND).
 - f. Craving for opioids, and for other drugs, measured by Visual Analog Scales (VAS).
 - g. Depressive, anxiety, and subacute withdrawal symptoms (typical constellation is fatigue, anorexia, and insomnia), as measured by the Hamilton Depression Scale (17-item) (HAM-D) and the Subjective Opioid Withdrawal Scale (SOWS).
 - h. Problems related to drug abuse, as measured by the Addiction Severity-Index-Lite (ASI-Lite) and EuroQol (EQ-5D).
 - i. HIV risk behavior over time, as measured by the Risk Assessment Battery (RAB).
 - j. Cognitive function, as measured by performance on brief pen and paper tasks (Trail Making Test Parts A and B, Stroop).
2. Explore baseline demographic, clinical, and genetic features as predictors of opioid use outcome over the 6-month trial (main effect of predictors), and as moderators of differential treatment effect (moderator by treatment interaction).
3. Collect a limited dataset to permit analyses of economic costs and benefits of the two treatments.

6.0 STUDY DESIGN

6.1 Overview of Protocol Study Design

This is a multi-center, two-arm, 6-month (24-week), parallel-group, open-label, randomized controlled trial to examine the comparative effectiveness and safety of XR-NTX versus BUP-NX. Candidates are individuals seeking treatment for opioid dependence (heroin or prescription opioids) who are admitted to an inpatient (detoxification and/or short term residential treatment) program for treatment of substance dependence. The study is conducted in 8 CTPs that: (a) provide or partner with opioid detoxification services (inpatient/residential) which have the capacity to maintain participants opioid-free, (b) have the capacity to initiate patients onto XR-NTX or BUP-NX, (c) have the capacity to maintain participants on XR-NTX or BUP-NX for the duration of the 24-week trial, (d) have a sufficient flow of patients completing detoxification and who do not routinely receive long-term medication-assisted therapy as to provide a sufficient population of potential participants to achieve study enrollment goals, and (e) can provide a minimum level of outpatient care (at least one group and/or individual counseling session per week) for 24 weeks. Candidates are consented, screened, and randomized at the time of admission, during detoxification or during early abstinence. Participants meeting all eligibility criteria are randomized to one of two treatment conditions, XR-NTX or BUP-NX. Treatment is for 24 weeks in the context of a protocol-directed medical management treatment program and individual or group psychosocial counseling. Research visits occur weekly, until relapse criteria are met, for collection of urine samples and safety and other assessments. XR-NTX is administered by injection on an approximately every-four-week basis; BUP-NX is provided for take-home, initially on a weekly basis, transitioning to an every-two-week and then to an every-four-week schedule. Medical management for both conditions is on a similar (weekly, transitioning to every-two-weeks, to every-four-weeks) schedule. The primary outcome measure is the time to the event of relapse. XR-NTX is provided as Vivitrol®. BUP-NX is provided as Suboxone® film.

The Protocol will proceed in four phases (see Figure 1).

Phase 1: Informed Consent, Screening, and Randomization (Days -15 through Day 0): This phase begins with informed consent during the index admission, and initiates enrollment, the conduct of all study-specific procedures and the collection of study data. During the first several days of an index admission, clinical and/or research staff provide information about the study to potential participants (for scheduled admissions this information may be provided in advance of the admission). Guidelines for opioid detoxification are provided in the study MOP; data on detoxification utilization are collected. This phase may take place from 1 day up to 15 days. Following final review and confirmation of all eligibility criteria, randomization may proceed. Randomization may take place on the same day as informed consent and screening if recent liver function results are available, but in most cases takes place 2 or 3 days later. Regardless of when randomization takes place, the date of randomization is defined as “Day 0”.

Phase 2: Induction (Day 0 through Day 156): Following randomization, participants are inducted onto their assigned active medication condition and treated as outpatients for 24 weeks per protocol. Guidelines for induction onto XR-NTX and onto BUP-NX are provided in the study MOP. Following induction, XR-NTX is administered by injection approximately every 4 weeks; and BUP-NX is quickly titrated upwards to maintenance doses. Induction should occur as soon as practicable following randomization, but may occur as late as week 22. Participants continue into Phases 3 and 4 for research visits, even if not yet inducted onto their assigned medication.

Phase 3: Active Treatment (Week 1 through Week 24): Following randomization, participants are inducted as soon as practicable and treated per their assigned active medication condition

and followed as outpatients until 24 weeks post-randomization. Assessment visits occur weekly until relapse criteria are met. Participants whose induction onto their assigned study medication is delayed will also attend weekly research visits. Medical management visits will initially occur weekly, transition to every two weeks and then to every four weeks. In order to retain participants in treatment, and consistent with good practice, we permit flexibility with dosing (see section 8.5). The window for Visit 1 is -3/+6 days to accommodate induction; however, induction may occur after Visit 1. A +/- 3-day window is permissible for subsequent weekly visits. For participants who relapse and/or become lost to follow up, a -3/+28 day window is permissible to complete the EOT visit. Participants who relapse will discontinue study medication and weekly research visits, but should be encouraged to attend the week 24 and follow up visits at weeks 28 and 36.

Phase 4: Post Treatment Follow-up (Week 25 through Week 36): Toward the end of the 24-week treatment period, participants are referred for follow-up care in the community (which could include continuation of medication, if available, indicated, and desired), and follow-up outcomes are assessed at week 28 and week 36 post-randomization. For participants receiving BUP-NX, who do not wish to continue, or for whom community resources are not available, the study provides a two-week BUP-NX taper. A -3/+28 day window is permissible for the scheduled week 28 visit and a +/- 4 week window is permissible for the scheduled week 36 visit.

6.2 Treatment Initiation

To maximize generalizability, this study is designed to permit entry of participants throughout opioid detoxification and early abstinence. While XR-NTX can only be administered to individuals who have completed detoxification, the percentage of participants who are randomized early that are able to successfully initiate antagonist therapy is unknown. A risk to this study plan is that a differentially large percentage of individuals may be unable to initiate XR-NTX versus buprenorphine therapy. The study includes an adaptive strategy such that if at a single time point a statistically lower treatment initiation rate is observed in “early” entry cases, then the study will be revised to:

- (a) Exclude further early entry cases and analyze them separately; and
- (b) Expand the total accrual target to maintain the initial design power for the late entry cases.

This assessment occurred after the entry of 100 cases randomized early in the detoxification process (e.g., prior to 3 opioid-free days).

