Beyond a sample size of 150 to 200 patients per group, further increments in sample size (200 per group, 250 per group, 300 per group, etc.) yield diminishing returns in terms of only relatively small further narrowing of the 95% confidence interval. The rationale for increasing the total sample size to N ~600, in the event of a significant difference in induction success rate among early randomizers, is that given the current ratio of early to late randomizers, N ~600 total will yield approximately 250 early randomizers and 350 later randomizers. 350 late randomizers (N = 175 per treatment group) is close to the 400 (N = 200 per group) originally planned, and will yield a very similar (only slightly wider) 95% confidence interval. This will preserve the intent to achieve a relatively precise estimate of the difference in relapse rates among late randomizers.

Simulation results for the 50th and Upper 95th percentile of the 95% Confidence Interval Widths for the Hazard Ratio, selected sample sizes with lambda=0 and lambda=0.678

The decision theoretic properties of n=200/arm is evaluated further under a decision theoretic approach and using the logrank test. With two-sided alpha = 0.05, N = 400 total participants

provides 90% power to detect a hazard ratio of .63 for the second treatment. Table 4 provides additional characterization of power characteristics of the sample size.

Table 4. Detectable Alternatives and Power for 2-tailed 5% level logrank test without censoring Null distribution has a 40% 6 month success rate, N1=N2=200

Power (%)	Hazard Ratio	6 Month Survival Rate (%) under the Alternative
90.0	.633	56.0
80.0	.678	53.8

Note that inclusion of the baseline level of opioid dependence severity stratification variable in the statistical model as a covariate may increase power and narrow the confidence limits on treatment hazard ratios, should divergent success rates be present in the strata groupings.

Secondary analyses of moderators of treatment effect are important to trial sample size selection. With 200 XR-NTX cases evenly split between 2 levels of a classifying variable, we would have 79% power to detect, using a 2-tailed 5% level test of a binary endpoint, a 20 percentage point difference between the groups. Thus the selected sample size would be relatively robust in its ability to determine whether there are important differences in therapeutic success rates for major demographic or baseline clinical factors.

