12.3 Study modification for differential treatment initiation

To maximize generalizability, this study has been designed to permit entry of participants throughout the opiate detoxification process and early abstinence. At the time the study was designed it was understood that community-based practice of detoxification and medication induction would vary across sites and across patients within sites. It was further decided that the protocol would allow this variation in community based practice of detoxification-induction, consistent with the aims of an effectiveness trial to test the medications under real world conditions. It was also anticipated that induction onto BUP-NX would be easier than induction onto XR-NTX for patients who are randomized “early” while opioids are still in their system. This is because BUP-NX can be safely initiated while opioids are still in the system, as long as some signs of withdrawal begin to develop, while for XR-NTX one needs to wait until detoxification is completed and this delay is an opportunity for attrition. The concern is that a higher induction failure rate on XR-NTX, among those randomized early will contribute to differences in outcome (time-to-relapse) across the 6 month trial, with induction failure leading to relapse. If this is the case, then the interaction between early vs. late randomization and treatment assignment on the primary outcome (time to relapse) becomes germane.

Therefore, after the entry of 100 “early randomizers” (as defined in Section 8.3) we will compare the induction success rate in these early randomizers on XR-NTX vs. BUP-NX with a test of difference between proportions. The decision rule has >80% power ($\alpha=2.5\%$ 1 tail) to identify differences of .25 or greater if the true initiation rate for the BUP-NX is in the expected range ($\geq .85$). If the difference in induction failure rate is significant, then:

1. Increase the sample size to end enrollment at such time as 350 late randomizers have been enrolled to increase power to estimate the difference in primary outcome (time-to-relapse) in this late randomizer group. It is projected that at such time the total N will be approximately 600.
2. Amend the data analysis plan (Section 12.4 of the protocol).

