12.7 Interim Analyses

The study will undergo safety monitoring by the designated DSMB. Both therapies are standard therapies with regulatory approval for treatment of opiate abuse. The treatment strategies have not been directly compared before and classic interim efficacy monitoring is not planned as both are considered acceptable therapies. An adaptive strategy for addressing substantial differential treatment acceptance is described above. Continuing the study until 350 late randomizers are included in the main analysis group will assist better understanding of personalized therapeutic strategies by making precise secondary assessments and identification of subgroups that differentially benefit possible.

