If the data analysis modification is implemented, the binary baseline variable (early vs. later randomization as previously defined) is included in the primary outcome analysis (outcome = time-to-relapse) as a covariate, a priori. The early vs. late randomization covariate by treatment interaction is included in the primary outcome analysis. If the covariate (early vs. late randomization) by treatment interaction is significant at $P < .10$, then the interaction term is retained in the final model. To characterize the interaction, the effect of treatment assignment (which includes the interaction and the main effect for treatment) (i.e., the difference in time-to-relapse between treatments) is estimated separately in early vs. late randomizers, and these two separate estimates become the primary findings of the study. If the covariate (early vs. late randomization) by treatment interaction is not significant ($p \geq .10$) then the interaction term will be removed from the model and the main effect estimate will be the primary finding of the study. Exploratory analyses will also evaluate whether the primary outcome measure of time-to-relapse is associated with the number of hours between last licit or illicit opioid use and randomization, that is, a continuous measure of the randomization timing. Both linear and non-linear effects will be explored as potential effect modifiers.

The Cox proportional hazard model is based on the following assumptions. First, there is a proportional hazards assumption, such that if an individual has a risk to opioid use at initial time point that is twice as high as that of another individual, then at all later times the risk of opioid use remains twice as high. Secondly, factors such as the way participants are recruited into a study and the determination of relapse remains constant over the period of the study i.e. censoring should be independent of an event (relapse) happening. The proportional hazards assumption will be assessed by testing of the time to relapse variable and the corresponding covariates of interest. If the proportional hazards assumption is not met, the final model will incorporate a time-dependent variable for the non-proportional predictors in the Cox model.

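### Protocol 6.2 describes a different triggered modification from Protocol 12.2–12.4 and SAP 5.3.3, and promises late-entry power that 175 per arm does not give

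*Protocol*

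**What the plan says.** Protocol 6.2 (Treatment Initiation) attaches two consequences to a statistically lower initiation rate among early entrants:

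- (a) "Exclude further early entry cases and analyze them separately"
- (b) "Expand the total accrual target to maintain the initial design power for the late entry cases"

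Protocol 12.2 gives the original design as 200 per arm, 400 in total. For the modified design it says that "N ~600 total will yield approximately 250 early randomizers and 350 later randomizers", and that "350 late randomizers (N = 175 per treatment group) is close to the 400 (N = 200 per group) originally planned". On the strength of this it claims a confidence interval only a little wider than planned. Protocol 12.3 gives the enrolment instruction: "Increase the sample size to end enrollment at such time as 350 late randomizers have been enrolled". Protocol 12.7 repeats it: "Continuing the study until 350 late randomizers are included in the main analysis group".

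On analysis, Protocol 12.4 and SAP 5.3.3 put randomization timing and its interaction with treatment into the primary model. If the interaction has P < .10, the treatment effect is estimated separately in early and late randomizers and "these two separate estimates become the primary findings of the study". If not, SAP 5.3.3 adds that "the interaction term will be removed from the model and the main effect estimate will be the primary finding of the study".

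SAP 5.3.3 also records that the modification has been triggered.

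**The concern.** For one trigger, the protocol gives two enrolment rules, two analysis rules and two accounts of what the late set will deliver. Section 6.2 is current body text, not an amendment log. It even reports in the past tense that the assessment took place, so it cannot be set aside as superseded.

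The practical risk lies in how the finished trial is read. Someone checking conduct against 6.2 would expect early entry to have stopped after the assessment, a separate analysis of early cases with no test attached, and undiminished power in the late set. Someone checking against 12.2–12.4 would expect early entry to continue, a split only on a P < .10 interaction, and slightly less precision. If the split estimates become the primary findings, the only power table in either document describes 200 per arm, which is not the size of the late set.

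**Working it through.** **Enrolment.** At the projected ratio of 250 early to 350 late, the 100 early cases that prompt the assessment come with about 100 × 350/250 = 140 late cases. If early entry stopped there, the total would be about 100 + 350 = 450, or 100 + 400 = 500 with 200 late per arm. A total of about 600 is reached only if early entry continues to about 250. So 6.2(a) and the figure in 12.2 and 12.3 cannot both describe the same trial.

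**Analysis.**

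| Place | When early and late are estimated separately |
|---|---|
| Protocol 6.2(a) | No condition stated |
| Protocol 2.0, 4.1; SAP 1.3.1 | If the treatment effect differs by timing |
| Protocol 12.4; SAP 5.3.3 | If the interaction has P < .10 |
| SAP 5.3.3, otherwise | Not separated; one main effect |

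**Power: inputs.** From Protocol 12.2 and Table 4 (repeated in SAP 3.3 and Table 2): two-sided alpha .05; reference 6-month success s = .40; exponential failure; no censoring before 6 months; hazard ratios .633 (90% power) and .678 (80% power) at 200 per arm. The late set has 350, or 175 per arm, as 12.2 states.

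**Formula (Freedman).** Expected events D = n(1 − s) + n(1 − s^HR). Power = Φ(√D × (1 − HR)/(1 + HR) − 1.96).

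**Reproducing Table 4 at n = 200.**

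- HR .633: .40^.633 = .560; D = 120 + 88.0 = 208.0; √208.0 × .367/1.633 − 1.96 = 1.28; power 90.0%.
- HR .678: .40^.678 = .537; D = 120 + 92.5 = 212.5; √212.5 × .322/1.678 − 1.96 = 0.84; power 79.9%.

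Both agree with the stated 90% and 80%.

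**Late set at n = 175.**

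- HR .633: D = 182.0; √182.0 × .2247 − 1.96 = 1.07; power 85.8%.
- HR .678: D = 186.0; √186.0 × .1919 − 1.96 = 0.66; power 74.4%.

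| Method | 200/arm, HR .633 / .678 | 175/arm, HR .633 / .678 |
|---|---|---|
| Freedman | 90.0% / 79.9% | 85.8% / 74.4% |
| Schoenfeld | 91.0% / 80.9% | 87.0% / 75.5% |
| Logrank simulation (20,000 runs) | 90.9% / 80.9% | 86.7% / 75.3% |

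Each method loses about 4 points at HR .633 and 5.5 points at HR .678. By Freedman, the hazard ratio detectable with 90% power moves from .633 to .611, and with 80% power from .678 to .658. Keeping the Table 4 power at its hazard ratios needs about 193 to 196 per arm by Schoenfeld or 201 by Freedman, so roughly 390 to 400 late randomizers rather than 350.

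**Precision.** The log hazard ratio interval widens by √(200/175) = 1.069, about 7%. That fits the wording of 12.2.

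**The case against.** The strongest reply is that only the two bullets in 6.2 are out of line. The synopsis, Protocol 4.1, 12.2–12.4 and 12.7, and SAP 1.3.1, 3.2 and 5.3.3 all state the operative rule or fit it. SAP 1.3 repeats the 6.2 paragraph and leaves both bullets out. SAP 5.3.3 specifies the model, the threshold and the fallback. All of that stands. A reader might infer from 6.2 that the primary analysis is undefined, or that enrolling early cases after the trigger breached the protocol. The documents do not support either inference, because 12.3 and SAP 3.2 direct exactly that enrolment.

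The second reply is that the design rests on precision. Section 12.2 chose 200 per arm on interval width, Protocol 12.5 puts estimation first, and 12.2 is open about the late set being smaller. That also stands: there is no arithmetic error in 12.2, and Table 4 is correctly labelled for the original design. If the interaction is dropped, the full set of about 300 per arm has more power than Table 4 states (97.8% and 92.9% by the same formula). But 6.2(b) makes its promise in terms of power, and for late entrants, and 350 does not meet it.

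Three stronger readings should be resisted:

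- That 6.2 requires separate analysis always. It says so without a condition; it does not exclude one.
- That 6.2 fixes a total of 450 to 500. It gives no number; those totals are inferred.
- That the late set really has 78.5% and 66.1% power, the figures at 175 per arm and 50% reference success. At 50% success 200 per arm already falls to 83.6% and 71.9%, so much of that gap comes from changing the success rate, not from 350 in place of 400.

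**Conclusion.** The inconsistency is real and should be corrected, at low priority. Section 6.2 conflicts with Protocol 12.2–12.4 and SAP 5.3.3 on whether early entry continues and on when early and late estimates are separated, and it claims a late-set power that the 350 target does not deliver. The shortfall is about 4 to 5.5 points: roughly 86–87% and 74–76%, against 90% and 80%.

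These figures assume an even split of the 350, the 40% reference success of Table 4, and an unadjusted logrank test. The primary analysis is a Cox model with site, severity stratum and timing, so they are a like-for-like comparison with Table 4 and not the exact power of that model. Section 12.2 set 40% below the roughly 50% seen elsewhere because early randomization was expected to raise failures. Success in a late-only set may therefore be higher, with fewer events and somewhat less power at a fixed hazard ratio. The documents give no late-only rate.

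**What to change.** - Rewrite 6.2(a) to agree with 12.2–12.4 and SAP 5.3.3: enrolment of both groups continues until 350 late randomizers are in (about 600 in total); timing and its interaction with treatment enter the primary model; early and late estimates are separated if the interaction has P < .10, and otherwise the main effect is the primary finding.
- Replace the promise in 6.2(b) with a statement that precision for late entrants stays close to the original design, at about 175 per arm.
- Add one late-set row to Protocol Table 4 and SAP Table 2: 175 per arm, about 86% at HR .633 and 74% at HR .678, on the same 40% assumption. Note that late-only success may be higher, for the reason 12.2 gives.
- Optional, for the record: the power above 80% quoted for the induction comparison (Protocol 12.3, SAP 3.2) holds for an uncorrected z test, about 82% at .85 against .60 with 50 per arm assumed. Under the Fisher's exact test named in SAP 5.2.2 it is about 76%. The rule has already triggered, so no decision changes.

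The cost is text and one table row in each document. It needs no further participants and changes neither conduct nor the SAP model. The price is stating a power for the late set below 90% and 80%.
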